11.1.1 Timing of Primary Analysis

The primary efficacy analysis will be conducted when all patients who were randomized on or before 03 March 2020 completes up to 12 weeks of treatment and follow up (see primary efficacy population of Section 10.4). Based on this enrollment cut-off date, 207 patients will be included in the PEP.

The safety analysis will be performed on safety population. . The results will be generated based on final database lock.

11.2. Secondary Endpoint Analysis

To maintain the trial-wise Type I error rate at 0.05, a closed test procedure will be used for the secondary endpoints. For efficacy analyses, the first date of assessment of 100% re-epithelialization of the wound surface without detectable exudate or visible non-epidermal tissue will be used.

The order of the endpoints to be assessed will be as follows:

- Proportion of subjects with confirmed complete wound closure of the study ulcer during the 12-week Treatment Phase as assessed by computerized planimetry, during the Treatment Phase

A point estimate will be presented along with the exact 95% confidence interval based on the binomial distribution.

- Time to complete wound closure, as assessed by the Investigator.

The endpoint will be summarized by descriptive statistics. In addition, duration of time to complete wound closure/healed will be analyzed as a time-to-event endpoint. The survival curves will be estimated using the Kaplan-Meier method and compared using the log-rank test.

The derivations of time to complete wound closure/healed will be listed for each patient.

- Time to complete wound closure, as assessed by computerized planimetry.

The endpoint will be summarized by descriptive statistics. In addition, duration of time to complete wound closure/healed will also be analyzed as a time-to-event endpoint. The survival curves will be estimated using Kaplan-Meier method and compared using the log-rank test.

The derivations of time to complete wound closure will be listed for each patient.

- Rate of complete wound closure as assessed by computerized planimetry

11.3. Exploratory Endpoint Analysis

An exploratory analysis will be performed to assess costs associated with the management of DFUs for the active and control groups using MRU data and standardized direct and in-direct unit costs. Additionally, wound closure status at the 4-week follow up visit will be evaluated.

11.4. Prognostic Factors Assessments

For the ITT population, a covariate analysis will be conducted to assess the impact of various prognostic factors on ulcer closure and to demonstrate the robustness of the primary efficacy analysis. Prognostic factors (i.e., covariates) will be included if they are found to be contributing factors (i.e., the individual covariate p-value is less than 0.05). Potential prognostic factors to be considered include:

Baseline ulcer size	Diabetes type
Age of ulcer at baseline	Race
Gender	Nicotine Use
Recorded HbA1c	Baseline BMI
Ulcer volume	Ulcer location

Additional planned analyses include the use of Analysis of Covariance (ANCOVA) models which incorporate consideration of stratification factors (i.e., site and baseline ulcer area) to compare reduction in study ulcer size between the two treatment groups and Kaplan-Meier analysis to assess and describe the differences in the time to wound closure in the two treatment groups.

11.5. Treatment Failures

Subjects who are withdrawn or discontinue during the Treatment Phase and/or who do not achieve complete wound closure during the Treatment Phase will not be replaced and will be considered treatment failures.

11.6. Missing Data

For efficacy evaluation data points, the last available observation (LOCF) will be used. In the analyses using the planimetry data, the last available planimetric value will be used for discontinued subjects. All subjects discontinued during the treatment period and before 100% wound closure during the treatment phase of the study will not be replaced and will be considered treatment failures for the primary and secondary endpoints evaluations.

12. DESCRIPTION OF OTHER VARIABLES AND ANALYSES

12.1. General Statistical Considerations

All collected study data will be presented in subject data listings. Statistical analyses will be performed using SAS® for Windows, version 9.2 or later. Descriptive statistics (n, mean, standard deviation, median, minimum and maximum) will be calculated by treatment group for continuous variables. Frequencies and percentages will be presented by treatment group for categorical variables.

12.2. Study Subjects

12.2.1. Discontinuations and Protocol Deviation

The disposition of all subjects who sign an ICF will be provided. The numbers of subjects screened, randomized, completed, and discontinued during the study, as well as the reasons for all post-randomization discontinuations will be summarized for each treatment group, for all centers combined and for each center separately. Disposition and reason for study discontinuation will also be provided as a by-subject listing.

Protocol Deviation data will be listed for each patient.

12.2.2. Demographic and Baseline Characteristics

Demographics and baseline characteristics will be summarized by treatment group using appropriate descriptive statistics. These variables include: Age of Ulcer at baseline, Gender, Race, Ethnic Origin, Substance Use, Baseline Ulcer Size, Diabetes Type, Nicotine Use, Recorded HbA1c, Baseline BMI, Ulcer Volume, and Ulcer Location. Meaningful differences between the treatment groups will be further explored to evaluate the impact, if any, on the study results.

Physical examination (including vitals) will be performed and data will be summarized using descriptive statistics.

12.2.3. Medical History

Medical History data will be listed for each patient.

12.3. Medical Resource Utilization

Data for below questions will be summarized using descriptive statistics by visit.

Since your last scheduled study visit, have you had any of the following visits related to DFU identified as the study ulcer?

1. Since the last scheduled study visit OR DFU related office visit, how much time have you or a care-giver (paid or unpaid e.g., family-member, friend, neighbor) spend on caring for the dressing changes on your study wound?
2. Since the last scheduled study visit OR DFRU related office visit, please answer the following questions related to off-loading:

3. Since the last scheduled study visit OR DFU related office visit, have you developed any NEW ulcers?
4. Since the last scheduled study visit OR DFU related office visit, have you purchased or rented any of the following equipment?
5. Since the last scheduled study visit OR DFU related office visit, how much have you had to spend out-of-pocket on the following items related to the treatment of your study wound?
6. Do you have government or private health care insurance?
7. Since the last scheduled study visit OR DFU related office visit, how much has the study ulcer limited your ability to do the following activities?
8. Since the last scheduled study visit OR DFU related office visit, please provide details about how your study ulcer has affected your participation in usual daily activities (e.g., school, work or other daily activities).

An exploratory analysis will be performed by an approved external vendor to assess costs associated with the management of DFUs for the active and control groups using medical resource utilization data and standardized direct and in-direct unit costs.

12.4. Ulcer Assessment

Data for below questions will be summarized by visit using descriptive statistics

- Ulcer Exudate Assessment
- Ulcer Infection Assessment
- Was picture of the study ulcer taken prior to debridement per protocol
- Ulcer Area
- Ulcer Size Reduction
- Is the Ulcer wound surface 100% re-epithelialized?
- Is the Ulcer wound surface without detectable exudate?
- Is the Ulcer wound surface without visible non-epidermal tissue?
- Extent of Ulceration
- Location of Study Ulcer
- Exudate Type
- Exudate Amount
- Ulcer Infection Assessment

- Ulcer Photography: Pre-Debridement
- Ulcer Measurement: Pre-Debridement.

12.5. Ulcer Treatment Procedure

Data for below questions will be summarized using descriptive statistics by visit.

- Sharp Debridement
- Ulcer Measurement
- PriMatrix Re-application
- Ulcer Photography
- PriMatrix Outer Dressings,
- Standard of Care Treatment,
- Dressing Supplies

12.6. Safety Analysis

Safety will be assessed through reports of adverse events and serious adverse events. Adverse Events related to the device, study ulcer and/or study procedures and all Serious Adverse Events will be recorded.

All safety parameters will be summarized descriptively by treatment. No inferential statistics are planned.

12.7. Adverse Events

Adverse Events will be coded using the MedDRA Medical Dictionary. AE's are defined as events with an onset after screening visit 1. Treatment Emergent AE's (TEAE) are defined as events with an onset on or after the randomized treatment. TEAEs will be summarized by treatment group, System Organ Class, and preferred term. The following TEAE summaries will be provided:

- TEAEs by severity grade
- TEAEs by relationship to study treatment.

In addition, separate summaries of Serious Adverse Events, and Adverse Events resulting in discontinuation of study treatment will be presented.

The safety population will be used for the safety analyses. Subjects will be counted only once for subject-based analysis. If the same event changes in severity for a subject, the worst severity will be reported.

An Adverse Event is considered treatment emergent if (1) it was not present at Screening Visit 1, and it is not a chronic condition that is part of the subject's medical history; or (2) it is present at Screening Visit 1 or as part of the subject's medical history, but the severity or frequency increases during treatment.

Treatment-emergent adverse events (TEAE) will be summarized for each treatment group by body system and preferred term. The severity of all adverse events will be determined by the investigator's judgment and classified as mild, moderate or severe.

Treatment groups will be compared with respect to the incidence of Adverse Events (all and TEAEs) and the proportion of subjects withdrawing from the study for Adverse Events by reason of withdrawal. Comparisons will be made overall, by body system and by preferred term and will be further categorized by severity and by study device relationship.

12.8. Supportive Analysis

To assess the robustness of the primary efficacy analysis results, supportive analysis will be conducted using the PP population. Statistical methodology for the supportive analyses will be the same as that of the primary analysis, except for the analysis population used. The PP population will be used for the supportive analysis while PEP will be used for the primary efficacy analysis.

13. STATISTICAL METHODS AND ISSUES

The statistical analysis will be performed by the Clinical Biostatistics Department and/or an approved external vendor.

13.1. Randomization

At the begininig of the study, site 109 had randomization issues due to data entry delay to the EDC. Eight (8) subjects were not randomized to their original treatment assignments per randomization date/time. A sensitivity analysis will be conducted to assess the impact on the randomization issue on the primary endpoint using the primary efficacy analysis population.

13.2. Methods of Analysis

13.2.1. Efficacy Endpoints

Confidence interval for proportions:

The method used to compute the two-sided 95% confidence interval (CI) for a single proportion will be the ‘exact’ method of Clopper and Pearson. For two proportions, the two-sided 95% CI for the proportion difference will be calculated based on the Z-test with continuity correction.

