6. SAMPLE SIZE DETERMINATION AND RATIONALE

This is a randomized study with two treatment groups. Assuming:

- 46% of DFUs receiving PriMatrix close by 12 weeks (84 days).
- 26% of DFUs receiving with Standard of Care close by 12 weeks (84 days).

Overall 2-sided Type I Error rate (alpha) of 0.05. Under the above assumptions, 102 subjects per treatment group will be required to meet the Type I error rate of 0.05 and 80% power; for a total

of 204 subjects for the study. As the treatment duration is short, the discontinuation rate is predicted to be around 15%. To accommodate the potential discontinuations, 240 subjects will be randomized (120 per treatment group) to this trial. The subjects will be randomized to the treatment groups in a 1:1 ratio.

A single interim analysis when 50% of subjects complete the trial, using group-sequential methods and Pocock alpha spending function, where the hypotheses will be tested at a two-sided alpha of 0.031 at the interim analysis and at a two-sided alpha of 0.028 at the final analysis.

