9. INTERIM ANALYSIS FOR SAMPLE SIZE ADJUSTMENT

9.1. Interim Prediction for Early Success

A single interim analysis will be performed when 50% of subjects complete the study. By employing a group-sequential design with a Pocock alpha spending function, the following decisions will be made at the interim analysis with respect to the efficacy outcome:

- 1) Stop the study upon demonstrating statistically significant superiority of the Active Treatment (PriMatrix Dermal Repair Scaffold) to the Control Treatment (Standard of Care) if the two-sided p-value testing the stated hypotheses is ≤ 0.031 and the difference is in favor of the Active Treatment (PriMatrix Dermal Repair Scaffold).
- 2) Stop the study upon demonstrating futility of the Active Treatment (PriMatrix Dermal Repair Scaffold) to the Control treatment (Standard of Care) if the two-sided p-value

testing the stated hypotheses is ≤ 0.031 and the difference is in favor of the Control Treatment (Standard of Care).

- 3) Continue the study if the two-sided p-value testing the stated hypotheses is > 0.031 .

With this design and assuming 46% of DFUs managed with the Active Treatment achieve complete wound closure by 12 weeks and 26% achieve complete wound closure when managed with the Control Treatment, the probability of stopping early due to showing superiority with the Active Treatment (PriMatrix Dermal Repair Scaffold) is 0.479. If the decision at the interim analysis is to continue the study, the hypotheses at the end of the study will be tested at a two-sided alpha level of 0.028 to maintain an overall two-sided alpha of 0.05.

Further, conditional power will be calculated at the interim analysis for predicting the final study success. In case more data is needed, sample size re-estimation will be considered in order to meet the final study objective.

Conditional Power

Conditional power: the probability of statistical significance at the completion of the study given the data obtained so far. From Jennison and Turnbull (2000) pages 205 to 208, the general upper one-sided conditional power at stage k for rejecting a null hypothesis about a parameter θ at the end of the study, given the observed test statistic, Z_k , is computed as

$$P_{uk}(\theta) = \Phi\left(\frac{Z_k \sqrt{I_k} - z_{1-\alpha} \sqrt{I_K} + \theta(I_K - I_k)}{\sqrt{I_K - I_k}}\right),$$

the general lower one-sided conditional power at stage k is computed as

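### The interval for the difference in closure rates is fixed at 95% while the final primary test is at two-sided 0.028, so the interval can exclude zero when the test fails; the level for the secondary tests at each look is not stated

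*SAP*

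**What the plan says.** - **Overall error and nominal levels (SAP 6).** The overall level is "Overall 2-sided Type I Error rate (alpha) of 0.05". The design is "A single interim analysis when 50% of subjects complete the trial, using group-sequential methods and Pocock alpha spending function", with testing "at a two-sided alpha of 0.031 at the interim analysis and at a two-sided alpha of 0.028 at the final analysis". SAP 9.1 repeats that, if the trial continues, the hypotheses "will be tested at a two-sided alpha level of 0.028 to maintain an overall two-sided alpha of 0.05". Protocol 8.3 and 8.6 agree.
- **Primary test (SAP 11.1).** The test is CMH on the primary efficacy population, which SAP 11.1.1 puts at 207 patients. No CMH strata are named. The only intervals in this section are exact 95% intervals for each arm's closure rate.
- **Interval for the difference (SAP 13.2.1).** "For two proportions, the two-sided 95% CI for the proportion difference will be calculated based on the Z-test with continuity correction".
- **Secondary endpoints (SAP 11.2).** "To maintain the trial-wise Type I error rate at 0.05, a closed test procedure will be used for the secondary endpoints". The endpoints are ordered. No nominal level is given for the interim or the final look, and gating on the primary is not stated. Protocol 8.12.1 has the same wording.

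Neither document ties the interval for the difference to 0.028 or calls it descriptive only.

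**The concern.** A two-sided test at 0.028 pairs with an interval of level 1 − 0.028 = 97.2%. A 95% interval is narrower, so some results with p a little above 0.028 will have an interval wholly above zero. The report would then show a failed primary test next to an interval that most readers take as evidence of superiority. In an open-label trial whose results may be published and used in regulatory submissions (protocol 13), that invites a claim the group-sequential design does not support.

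The secondary endpoints raise a related gap. The one figure attached to them is the trial-wise 0.05. An analyst could reasonably test each at 0.05 at whichever look ends the trial, or at 0.031 or 0.028, and the SAP does not settle which.

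**Working it through.** **1. The plan's own figures reproduce.** Inputs from SAP 6 and 9.1: overall two-sided 0.05, one look at half the information, 46% vs 26%, 102 per arm.
- Pocock-type spending at t = 0.5: 0.05 × ln(1 + (e − 1) × 0.5) = 0.0310. Solving the bivariate normal with correlation √0.5 gives a final level of 0.0277, which rounds to 0.028. The rounded pair gives 0.0502 overall.
- Drift at 102 per arm with pooled variance: 0.20 / √(2 × 0.36 × 0.64 / 102) = 2.98. The probability of an early superiority stop is 0.479, as stated, and power is 0.803.

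The final level of 0.028 is therefore correct for this design, and the matching interval uses z = 2.197 instead of 1.960.

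**2. One conflicting result.** Assumptions: the 207 patients split 104/103, and CMH is run in a single stratum. Take 42/104 vs 27/103.
- CMH: total closures 69; expected in Active 104 × 69 / 207 = 34.67; variance 104 × 103 × 69 × 138 / (207² × 206) = 11.56; χ² = (42 − 34.67)² / 11.56 = 4.65; p = 0.031. The test fails at 0.028.
- Difference: 0.4038 − 0.2621 = 0.1417. Unpooled SE = 0.0648. Continuity correction (1/104 + 1/103)/2 = 0.0097.
- Planned 95% interval: 0.1417 ± (1.960 × 0.0648 + 0.0097) = 0.005 to 0.278. It excludes zero.
- The corrected 97.2% lower limit is −0.010.

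Other cases: 41/104 vs 26/103 has p = 0.0296 and interval 0.006 to 0.277; 45/104 vs 30/103 has p = 0.035 and interval 0.002 to 0.281.

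**3. How often.** Exact binomial enumeration of all outcomes at 104/103, giving the probability that the interval lies above zero while p > 0.028:

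| True rates | 95%, corrected (plan) | 95%, uncorrected | 97.2%, corrected | 97.2%, uncorrected |
|---|---|---|---|---|
| 46% vs 26% | 3.3% | 6.8% | 0 | 0.7% |
| 40% vs 26% | 5.0% | 10.8% | 0 | 1.5% |
| 36% vs 26% | 4.0% | 9.2% | 0 | 1.3% |
| 26% vs 26% | 0.4% | 1.2% | 0 | 0.1% |

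The correction already removes about half of the conflict at 95%. At 97.2% it removes all of it in this direction. It then produces the reverse conflict (test passes, interval includes zero) in about 3% to 4% of trials at the three effects shown.

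**4. Width.** At 46% vs 26%, SE = √(0.46 × 0.54/104 + 0.26 × 0.74/103) = 0.0652. Planned half-width: 1.960 × 0.0652 + 0.0097 = 13.8 points. At 97.2% uncorrected: 2.197 × 0.0652 = 14.3 points, about 4% wider.

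**5. Secondary tests, if run at 0.05.** Simulation of a true-null secondary, gated on the primary at 0.031/0.028 and tested at 0.05 at the look where the primary succeeds. The correlation with the primary is an assumption; the documents give none. The maximum one-sided false-positive rate in favor of Active, over the size of the primary effect, is:
- correlation 0.5: 2.7%
- correlation 0.9: 3.4%
- correlation 1.0: about 4%

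The reference is 2.5%. Near the planned effect (drift about 2.8 to 3) the rate is about 2.6% to 2.7%. The two-sided rate peaks at 3.9% at correlation 0.9. It passes 5% only at correlation 1 with almost no primary effect (5.5% at drift 0.25). With 0.031/0.028 for the secondary as well, the one-sided rate stays at about 2.5% or below.

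**The case against.** The strongest reply is that nothing is decided by the interval. SAP 6 and 9.1 decide on the p-value, and no section uses an interval to declare success. That stands. A reader might infer that the primary type I error is inflated; it is not. Overall error would rise to 0.0686 only if the final result were judged at 0.05 after a 0.031 interim look, and the plan does not do that.

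Second, SAP 13.2.1 is a general methods entry, and the primary section names only per-arm intervals, for which excluding zero is beside the point. A conventional 95% interval shown descriptively beside a group-sequential test is common. This limits the weight of the point but does not remove it: 13.2.1 is headed as efficacy methods, the primary comparison is of two proportions, and the word descriptive is not there.

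Third, the size is modest. For 25 of the 30 control counts from 15 to 44, one active count gives the conflict, which sounds like a high frequency. It counts rows of a table, one cell in each; the probabilities above are the right measure.

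Fourth, a reader might infer that the secondary tests break the stated trial-wise 0.05. The SAP does not support this. It never says that each secondary is tested at 0.05, and the stated rate is two-sided. Under gating the two-sided rate stays below 5% except in the extreme case shown. What can be said is that the level is not stated, and that one permissible reading exceeds 2.5% in the direction that matters.

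Finally, one might object that the interval is unstratified while CMH is stratified. SAP 11.1 names no strata, so this mismatch cannot be established from the documents.

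**Conclusion.** The mismatch is real and can occur at the planned analysis size. The interval for the difference is at 95%, the final test is at 0.028, and the two can disagree toward apparent success with probability about 3% at the design rates, 5% at 40% vs 26% and 0.4% with no effect. These figures assume a 104/103 split and a single-stratum CMH test; stratification would shift individual p-values but would not close the gap between 95% and 97.2%. They also take the final level as 0.028, as the plan is written; the documents do not say whether the interim look took place.

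This is a fault of reporting and interpretation, not of primary error control. For the secondary endpoints the supported conclusion is an omission: the gating and the nominal level at each look are not stated. It is worth correcting because the correction is nearly free.

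**What to change.** - **SAP 13.2.1.** Report the risk difference with an interval at 1 minus the alpha used at that look: 97.2% at the final 0.028, or 96.9% if the trial stops at the interim 0.031. Build it to match the CMH test and the strata that test uses, which SAP 11.1 should name. Label any 95% interval for the difference as descriptive. The per-arm exact 95% intervals can stay.
- **Continuity correction.** Choose it deliberately. Keeping it at 97.2% trades one conflict for the other. Dropping it leaves a residual discordance of about 1% at the effects tried, because a Wald interval and the CMH test use different variances.
- **SAP 11.2.** State that the ordered secondary tests are performed only if the primary succeeds, and that each uses the primary's level at that look (0.031 or 0.028).

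The cost is SAP wording and an interval about 4% wider (half-width about 14.3 instead of 13.8 points at 46% vs 26%). No change to the sample size or to the primary decision rule is needed.
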